#### **14.6.3. Dose evaluation visit 2**

Two to five days after dose evaluation visit 1, if the dose of enalapril was increased, the patient should return for a second dose evaluation visit. Blood pressure and U&Es should be measured and the patient should be assessed for side effects.

If the patient has systolic BP  $\geq 100$  mmHg, normal serum potassium (potassium  $< 5.5$  mmol/L), and stable renal function (serum creatinine  $< 30$   $\mu\text{mol/L}$  increase since last assessment, or a  $< 1.5$  times increase from baseline) then the enalapril dose should be up-titrated to 10mg BD.

If the patient is, in the clinical opinion of the investigator, unlikely to tolerate a higher dose, then the dose should remain the same.

If the patient has a  $\geq 30$   $\mu\text{mol/L}$  increase in serum creatinine levels since the last assessment, or a  $\geq 1.5$  times increase from baseline, potassium  $\geq 5.5\text{mmol/L}$ , or symptomatic hypotension (SBP  $< 100\text{mmHg}$ ) then reduce back to previously tolerated dose and recheck blood pressure, and U&Es two to five days later.

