#### **13.2.9. Urea and Electrolytes (U&Es)**

U&Es (Urea, Na+, K+ and Creatinine) will be assessed at baseline, at each dose evaluation visit (enalapril arm only), and within 72 hours prior to the intended day 1 at the start of chemotherapy at cycle 2, 3, 4, 5, 6 and at one month after the last epirubicin dose.

Samples will be collected, processed and analysed in accordance with local hospital practice, with the results recorded in the eCRF. These blood samples are often taken and tested routinely, if this is the case, and they fit within the windows for the trial, repeat tests specifically for the trial are not needed.

If serum creatinine levels increase by 30 µmol/L over 48-96 hours, or increases to >1.5 times the baseline value, the clinical judgement of the Principal Investigator should be sought, and/or the Chief Investigator, to confirm the action to be taken, which may require a temporary or permanent halt to enalapril (for those in the enalapril group).

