##### **14.6.2. Dose evaluation visit 1**

Two to five days after the start of enalapril, the patient should return for a dose evaluation visit. Blood pressure and U&Es should be measured and the patient should be assessed for side effects.

If the patient has systolic BP  $\geq$ 100 mmHg, normal serum potassium (potassium  $<$ 5.5 mmol/L), and stable renal function (serum creatinine  $<$ 30  $\mu$ mol/L increase from baseline over 48-96 hours) then the enalapril dose should be up-titrated to 5mg BD.

If the patient is, in the clinical opinion of the investigator, unlikely to tolerate a higher dose at this point then the dose should remain the same. At the discretion of the investigator, a further assessment at

dose evaluation visit 2 could be made to consider up-titration of enalapril to 5mg BD using the same criteria as above.

If the patient has a  $\geq 30$   $\mu\text{mol/L}$  increase in serum creatinine levels since the last assessment compared to baseline, new hyperkalaemia (potassium  $\geq 5.5\text{mmol/L}$ ), or symptomatic hypotension (SBP  $< 100\text{mmHg}$ ) then enalapril should be permanently discontinued and the patient withdrawn from the study. The patient should be seen again within 7 days to ensure the reasons for withdrawal have resolved to the satisfaction of the investigator.

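### At dose evaluation visit 2 (14.6.3), a patient who crosses exactly one of the two creatinine limits is told both to raise and to reduce enalapril

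*Combined protocol and SAP*

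**What the plan says.** Visit 2 takes place as follows: "Two to five days after dose evaluation visit 1, if the dose of enalapril was increased". A patient attending on that basis is therefore on 5mg BD. Section 14.6.3 then gives three instructions.

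- **Raise.** Systolic BP must be at least 100 mmHg, potassium below 5.5 mmol/L and renal function stable. Stable means a creatinine rise below 30 µmol/L "increase since last assessment, or a" rise below 1.5 times from baseline. The rule ends: "times increase from baseline) then the enalapril dose should be up-titrated to 10mg BD".
- **Hold.** The dose stays the same if the investigator thinks a higher one is unlikely to be tolerated.
- **Reduce.** One trigger is a 30 µmol/L or greater "increase in serum creatinine levels since the last assessment, or a" rise of 1.5 times or more from baseline. High potassium and symptomatic hypotension are the others. The action is: "then reduce back to previously tolerated dose and recheck blood pressure, and U&Es two to five days later".

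The neighbouring sections differ. Visit 1 (14.6.2) uses a single creatinine limit for the increase, a rise of less than 30 µmol/L: "increase from baseline over 48-96 hours) then the enalapril dose should be up-titrated to 5mg BD". Visit 3 (14.6.4) has no up-titration step. Section 13.2.9 separately calls for investigator judgement when creatinine rises by 30 µmol/L "over 48-96 hours, or increases to >1.5 times the baseline value".

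**The concern.** The opposite of 'below limit A or below limit B' is 'at or above A *and* at or above B'. The reduce rule instead says 'at or above A *or* at or above B', so the two rules are not complements. Anyone who crosses one limit but not the other satisfies both.

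The two actions point in opposite directions. From 5mg BD, one doubles the dose to 10mg BD and the other halves it to 2.5mg BD. Section 14.5 lists renal impairment among the important side effects of enalapril, so this rule protects patients directly. Four Trusts will apply it (9.4). Section 19.4 forbids planned deviations and treats frequent, repeated ones as a possible serious breach, yet for these patients any action departs from one written instruction.

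**Working it through.** **Inputs.** The limits, connectors and actions come from 14.6.3, the visit 1 entry condition from 14.6.2 and the review triggers from 13.2.9. The creatinine values are illustrative assumptions. The plan states no figure on this point, so there is none to reproduce.

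**Notation (µmol/L).** Let b be baseline, l visit 1 and c visit 2, with BP and potassium acceptable. A 1.5 times increase is read as reaching 1.5 × b, which is how 13.2.9 words it.

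- Raise, as written: c − l < 30 **or** c < 1.5b
- Reduce, as written: c − l ≥ 30 **or** c ≥ 1.5b
- Raise, corrected: c − l < 30 **and** c < 1.5b

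**Step 1: the four possible cases.**

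| Rise ≥ 30 | ≥ 1.5 × baseline | As written | With 'and' in the raise rule |
|---|---|---|---|
| no | no | raise | raise |
| no | yes | **raise and reduce** | reduce |
| yes | no | **raise and reduce** | reduce |
| yes | yes | reduce | reduce |

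**Step 2: such patients can reach visit 2.** Visit 1 requires only a rise below 30 from baseline.

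- *Fast rise*, 80 / 80 / 112: the visit 1 rise is 0, so the dose goes to 5mg BD. At visit 2, 112 − 80 = 32 and 112/80 = 1.40. Only the 30 µmol/L limit is crossed, so both rules apply.
- *Stepwise rise*, 70 / 90 / 110: the visit 1 rise is 20, so the dose goes to 5mg BD. At visit 2, 110 − 90 = 20 and 110/70 = 1.57. Only the 1.5 times limit is crossed, so both rules apply.

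**Step 3: width of the overlap.** The conflict runs from the smaller of l + 30 and 1.5b up to just below the larger. In whole numbers:

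| Baseline b | Visit 2 values meeting both rules, l = b | Visit 2 values meeting both rules, l = b + 20 |
|---|---|---|
| 50 | 75–79 | 75–99 |
| 60 | none (both limits are 90) | 90–109 |
| 70 | 100–104 | 105–119 |
| 80 | 110–119 | 120–129 |
| 100 | 130–149 | none (both limits are 150) |

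**Step 4: does 13.2.9 settle it?** Visit 2 falls two to five days, or 48–120 hours, after visit 1. The 30 µmol/L trigger in 13.2.9 covers 48–96 hours. Taken literally, the fast-rise patient seen on day 5 (120 hours, ratio 1.40) meets neither trigger. The stepwise patient does meet one, through 1.57 > 1.5. Even then, 13.2.9 asks for judgement on what to do and does not say which 14.6.3 instruction prevails.

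**Step 5: the other reading.** If a 1.5 times increase meant 2.5 × baseline, 70 / 90 / 110 would no longer conflict. The case 80 / 80 / 112 still would, since the rise is 32 and 112 < 2.5 × 80 = 200.

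**The case against.** The strongest reply is that no clinician would be misled. The limits explain what stable renal function means, and a patient who meets the same section's reduction trigger is hardly stable. Section 14.6.4 repeats the either-limit trigger for reduction, so the intended meaning is very probably 'and'. The opening of 14.6 makes clinical judgement part of setting the maximum tolerated dose. The investigator may hold the dose, and 13.2.9 names who decides in most of these cases. A patient who is increased is rechecked two to five days later, when either limit leads to reduction.

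Much of this stands. It makes harm less likely, and it shows that this is a wording inconsistency rather than a deliberate design choice. It does not supply a precedence. Holding the dose is a third action that still departs from the reduce instruction, and the visit 3 recheck comes only after the higher dose has been taken.

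A second reply is that the 48–96 hour window also appears in the visit 1 rule, where the visit is likewise at two to five days, so reading it strictly only in 13.2.9 is uneven. That is fair as far as it goes. If the window is read loosely, the day 5 fast-rise patient does reach 13.2.9 review. The conflict within 14.6.3 is the same either way.

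**Conclusion.** The concern holds. As written, 14.6.3 gives opposite dosing instructions to any patient with acceptable BP and potassium who crosses exactly one creatinine limit. The range of conflicting values depends on baseline and visit 1. It is empty at some combinations and 20 or more whole-number values wide at others, such as 130–149 at baseline 100 with no change at visit 1, or 75–99 at baseline 50 with visit 1 at 70.

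These ranges assume that the ratio limit means 1.5 × baseline. The logical conflict exists under either reading. The documents give no distribution of creatinine changes, so the number of affected patients cannot be estimated. The problem is confined to visit 2 and does not touch the sample size or the intention-to-treat primary analysis. It should be fixed because it is a renal-safety rule and the safeguards around it do not resolve it.

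**What to change.** In the up-titration criterion of 14.6.3, change 'or' to 'and': creatinine up by less than 30 µmol/L since the last assessment **and** below 1.5 times baseline. Crossing either limit then leads only to reduction, and the four-case table shows no overlap and no gap. Wording the ratio limit as in 13.2.9 would also remove the second reading.

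An optional sentence could say how the 13.2.9 review relates to the visit rules in 14.6.2 to 14.6.4; the one-word change works without it. Stopping at visit 1 but stepping back at visit 2 follows from the dose ladder and can stay.

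The cost is a short protocol amendment and a note to sites, with no new tests or visits.

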#### **14.6.4. Dose evaluation visit 3**

If the dose was increased at titration visit 2, the patient should return two to five days later, to have their blood pressure and U&Es rechecked to confirm that they are tolerating the enalapril.

If the patient has a  $\geq 30$   $\mu\text{mol/L}$  increase in serum creatinine levels since the last assessment, a  $\geq 1.5$  times increase from baseline, potassium  $\geq 5.5\text{mmol/L}$ , or symptomatic hypotension (SBP  $< 100\text{mmHg}$ ) then reduce back to previously tolerated dose and recheck blood pressure, and U&Es two to four days later.

If the patient is, in the clinical opinion of the investigator, tolerating the dose, then the dose should remain the same. If not, then the dose of enalapril should be reduced to the previously tolerated dose.

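### At dose evaluation visit 2, a patient who fails exactly one of the two creatinine tests is told both to go up to 10mg BD and to step the dose down

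*Combined protocol and SAP*

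**What the plan says.** Section 14.6.3 applies to patients whose dose was raised to 5mg BD at visit 1. It contains three instructions.

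- **Raise.** If systolic pressure is at least 100 mmHg, potassium is below 5.5 mmol/L and renal function is stable, the dose goes up. Stability is defined by two creatinine limits, below 30 µmol/L "increase since last assessment, or a" below-1.5 limit: "times increase from baseline) then the enalapril dose should be up-titrated to 10mg BD".
- **Hold.** The dose stays put if the investigator thinks the patient "unlikely to tolerate a higher dose, then the dose should remain the same".
- **Reduce.** If there is a 30 µmol/L or greater "increase in serum creatinine levels since the last assessment, or a" 1.5-or-greater change from baseline, or high potassium, or symptomatic hypotension, "then reduce back to previously tolerated dose and recheck blood pressure, and U&Es two to five days later".

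Two other sections use the same limits. Section 14.6.4 (visit 3) treats either creatinine limit alone as a reason to step down: "then reduce back to previously tolerated dose and recheck blood pressure, and U&Es two to four days later". Section 13.2.9 asks for investigator review if creatinine rises by 30 µmol/L over 48-96 hours, "or increases to >1.5 times the baseline value, the clinical judgement of the Principal Investigator should be sought".

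**The concern.** The reduce rule is meant to catch patients whom the raise rule should not reach. For that, one rule has to be the negation of the other. Negating an either-test-failed rule gives a both-tests-passed rule, but the raise sentence is written as either-test-passed. The two therefore overlap whenever the tests disagree, and section 14.6.3 gives no order of precedence.

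A patient at visit 2 is on 5mg BD, so the two sentences point to 10mg BD and 2.5mg BD, a fourfold difference in the dose taken next, for one laboratory result that has already crossed a named renal limit. Two sites could act in opposite ways and each cite the protocol. Section 19.4 requires deviations to be documented, yet a monitor would have no text for deciding which action complied.

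**Working it through.** **Inputs.** From section 14.6.3: test A is passed if visit 2 creatinine minus visit 1 creatinine is below 30 µmol/L; test B is passed if visit 2 creatinine is below 1.5 times baseline. Test B is read as a ratio to the baseline value, as section 13.2.9 puts it. Blood pressure and potassium are taken as acceptable. The documents give no creatinine distribution and no figure of their own to reproduce, so all creatinine values below are assumptions.

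**Step 1: truth table.** Raise = A or B. Reduce = (not A) or (not B).

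| A | B | Raise | Reduce |
|---|---|---|---|
| pass | pass | yes | no |
| pass | fail | yes | **yes** |
| fail | pass | yes | **yes** |
| fail | fail | no | yes |

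**Step 2: one example of each conflict.**

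- Baseline 80, visit 1 80, visit 2 112: rise 112 − 80 = 32 (A fails); ratio 112/80 = 1.40 (B passes). Both instructions apply.
- Baseline 60, visit 1 80, visit 2 95: rise 95 − 80 = 15 (A passes); ratio 95/60 = 1.58 (B fails). Both instructions apply.

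**Step 3: how wide the conflict is.** Test A starts to fail at visit 1 + 30, and test B at 1.5 × baseline. The conflict is the band between those points, of width |1.5 × baseline − visit 1 − 30|. In whole µmol/L:

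| Baseline | Visit 1 = baseline | Visit 1 = baseline + 15 |
|---|---|---|
| 60 | none | 90-104 |
| 70 | 100-104 | 105-114 |
| 80 | 110-119 | 120-124 |
| 90 | 120-134 | none |
| 100 | 130-149 | 145-149 |

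With visit 1 equal to baseline, a baseline of 50 gives 75-79, 120 gives 150-179 and 150 gives 180-224. Over these cases the band is 0 to 45 µmol/L wide.

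**Step 4: the other reading of test B.** If the text means a rise of 1.5 times baseline (a value of 2.5 times baseline), the overlap remains. With baseline and visit 1 at 80 it runs from 110 to 199.

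**Step 5: which sentence is out of line.** At visit 3 either limit alone means reduce. In section 13.2.9 either limit alone means review. At visit 1 (section 14.6.2) a rise of 30 µmol/L or more means stopping enalapril permanently. Only the visit 2 raise sentence lets a patient over one limit go up.

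**Step 6: check of the repair.** The grid is baseline 40-150, visit 1 rise 0-29 and visit 2 30-400: 111 × 30 × 371 = 1,235,430 combinations, not weighted by likelihood.

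| Wording | Meet both rules | Meet neither |
|---|---|---|
| As written, ratio reading | 51,325 | 0 |
| Raise if A and B, ratio stated in both sentences | 0 | 0 |
| Raise if A and B, ratio stated only in the raise sentence, reduce sentence read as a rise of 1.5 times baseline | 0 | 20,255 |

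The last row is why both sentences must change. With baseline 50, visit 1 75 and visit 2 80, the rise is 5 and the ratio is 1.6. The patient cannot be raised, but is not told to reduce either, because 80 is below 2.5 × 50 = 125.

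**Step 7: what section 13.2.9 catches.** Visit 2 falls two to five days (48-120 hours) after visit 1. Take visit 1 equal to baseline, and read the 30 µmol/L trigger as 30 or more. Within 48-96 hours, section 13.2.9 refers all 10 conflicting values at baseline 80. At 96-120 hours it refers none of the conflicting values at the tabulated baselines of 70 to 150, because every one of them is below 1.5 times baseline. It also misses a value of exactly 1.5 times baseline when the rise is under 30.

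**The case against.** The best defence is that intent can be recovered from the page and that no prescriber is forced to double the dose. The raise sentence is conditional on stable renal function, and a result at a named step-down limit would hardly be called stable. The hold clause in section 14.6.3, the role of clinical judgement in section 14.6 and the discretion over reductions in section 14.6.5 all allow caution. After a visit 2 increase, section 14.6.4 says "the patient should return two to five days later, to have their blood pressure and U&Es rechecked", with its own step-down rule. The conflict band is also narrow or empty at several ordinary baselines.

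Most of this stands, and it limits the practical risk. It does not remove the contradiction. The discretion clauses add options without saying which rule prevails, and the visit 3 recheck comes after the higher dose has been started.

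Three stronger readings are tempting and are not supported:

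- A reader might infer that the protocol compels an unsafe increase. It does not; the investigator may hold the dose.
- A reader might take 51,325 of 1,235,430 (about 4%) as a rate of affected patients. The grid is unweighted and shows only that the overlap exists.
- In the other direction, a reader might think that section 13.2.9 picks up nearly every conflicting result. That depends on visit 2 falling within 48-96 hours, and the section asks for judgement, not reduction.

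**Conclusion.** The point holds as an internal inconsistency in a safety dosing rule; it is not a disputed design choice. Whenever exactly one creatinine test is failed, with blood pressure and potassium acceptable, section 14.6.3 gives opposite instructions. This follows from the wording alone under either reading of the 1.5-times limit. The creatinine bands rest on assumed baselines and visit 1 values, and they show that the conflict can arise in a plausible range. How many patients would meet it cannot be derived from the documents. The primary analysis method, Fisher's exact test by randomised group, is unaffected. The wording should be corrected, because the rule is operative and the correction is cheap.

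**What to change.** In section 14.6.3:

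- **Raise** only if creatinine is up by less than 30 µmol/L on the previous visit AND is below 1.5 times the baseline value.
- **Reduce** if creatinine is up by 30 µmol/L or more on the previous visit OR is at or above 1.5 times the baseline value.

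Use the same multiple-of-baseline phrase in section 14.6.4. The visit 2 creatinine tests then become exact complements and match the visit 3 limits. Section 13.2.9 will still differ slightly: its ratio limit is strictly above 1.5, and its 30 µmol/L limit is tied to 48-96 hours. That is tolerable for a review trigger.

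The cost is a few words in two sections and a reminder to sites, with the sponsor classifying the amendment under section 19.11. No extra patients, visits or tests are needed.

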#### **14.6.4. Dose evaluation visit 3**

If the dose was increased at titration visit 2, the patient should return two to five days later, to have their blood pressure and U&Es rechecked to confirm that they are tolerating the enalapril.

If the patient has a  $\geq 30$   $\mu\text{mol/L}$  increase in serum creatinine levels since the last assessment, a  $\geq 1.5$  times increase from baseline, potassium  $\geq 5.5\text{mmol/L}$ , or symptomatic hypotension (SBP  $< 100\text{mmHg}$ ) then reduce back to previously tolerated dose and recheck blood pressure, and U&Es two to four days later.

If the patient is, in the clinical opinion of the investigator, tolerating the dose, then the dose should remain the same. If not, then the dose of enalapril should be reduced to the previously tolerated dose.

#### **14.6.5. Continuation of treatment with enalapril**

Once the patient is on their maximum tolerated dose of enalapril they should receive this dose daily throughout the trial (including on chemotherapy treatment days). There may be instances where a patient has side effects to their cancer, chemotherapy or to enalapril that require a temporary halt to

taking enalapril. Temporary halts of up to 7 days (14 doses) will be allowed within the trial. These should be noted and explained. Where this due to an intolerance of enalapril, only one temporary halt will be allowed. Where the intolerance has manifested as angioedema, then treatment with enalapril should be withdrawn.

Re-introduction of enalapril may be at the discretion of the local clinician. It is recommended that where temporary halts are due to chemotherapy-related toxicities, then reintroduction at the established MTD is acceptable. Where temporary halts have been due to renal instability then reintroduction at a dose lower than the MTD is recommended.

Dose reductions of enalapril in routine use would not be expected; in this study they will be allowed and at the discretion of the investigator.

Any re-introduction or dose adjustment of enalapril must be followed 2-5 days after the re-introduction/adjustment to assess blood pressure and U&Es.

At each attendance prior to the start of a new cycle of chemotherapy, patients will be asked about how much enalapril they have left and a new prescription dispensed if required.

#### **14.6.6. End of treatment with enalapril**

Enalapril will be continued during chemotherapy and stopped three weeks following the last epirubicin dose. Any unused drug will be returned to the clinical research team who will return this to Pharmacy for reconciliation.

#### **14.7. Adherence to enalapril**

Patients on the enalapril arm will be asked to record their intake of enalapril and any reasons for not taking the drug using the PROACT enalapril adherence pro-forma. Patients will be asked to return unused drug when they:

- Change dose
- Withdraw
- Discontinue enalapril per protocol at the end of the trial

## **15. Adjuvant Chemotherapy**

All randomised patients will receive their planned 6 cycles of chemotherapy according to usual practice within the recruiting centre. This includes all concomitant medication and procedures for the safe administration of cytotoxic chemotherapy.

### **15.1. Permitted Chemotherapy Regimens**

Two 6-cycle epirubicin-based chemotherapy regimens will be permitted within this trial. Patients with HER2 positive breast cancer will be permitted as long as they are planned to receive one of these regimens, and Trastuzumab is not planned to start within 4-weeks of the final epirubicin dose.

